B. Study Type and Design: This study is a longitudinal, repeated measures, double-blinded design with subjects randomly assigned to placebo, low (20 mg/d) or high (80 mg/d) atorvastatin therapy during a 12-week aerobic exercise training protocol. We expect to screen approximately 150 participants to enroll (randomize) a maximum of 80 participants. The overall goal is to have 60 participants complete all study procedures (20 in each group). Repeated measures design allows each subject to serve as their own control. Placebo groups are included to account for potential changes in muscle mitochondrial function independent of statin therapy over the 1 year dose-response.

C. Sample size, statistical methods, and power calculation: The randomization for study drugs will be carried out by the biostatistician using a computer-based random number generator at a 1:1:1 allocation. Sample size for the study is powered on the basis of detecting a difference in VO₂peak between the EX+Plac group and the EX+Atorva80 group as well as between the EX+Atorva20 group and the EX+Atorva80 group at 12 weeks post-treatment. In our previously published study(13) (Table 2) the EX only group had a mean 2.6 ml/kg/min increase in VO₂peak following 12 weeks of training while the EX+Statin group only had a 0.4 ml/kg/min increase in VO₂peak. The estimated effect size of between group differences is 0.9 (Cohen's d). The increase of VO₂peak in the EX+Atorva20 group is expected

to be similar to that of EX+Plac group. A sample size of 35 per group provides 80% of power of detecting an effect size of 0.75 for a two-sided, two-sample t-test at 0.025 levels. Here, we use 0.025 for each group comparison to maintain the overall type I error rate at 0.05 level using Bonferroni correction. Assuming variances similar to what was observed in the pilot study, this study is powered to detect a difference of 1.53 ml/kg/min VO₂peak between groups. These power calculations led to a desired final sample size of 105 (35/group). We plan an enrollment of 120 (40/group) subjects to account for 10% dropout rate. The subject enrollment will be split equally between the two sites. As an exploratory analysis, the mean difference of VO₂peak (EX+ Atorva20- EX+ placebo) and its 95% confidence interval (CI) will be estimated. If the lower bound of the 95% confidence interval is greater than -0.8 ml/kg/min, EX+ Atorva20 will be considered non-inferior to EX+ placebo.

D. Subject Criteria

[figure not shown]

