a. Inclusion criteria/Exclusion criteria:

- i. Inclusion Criteria
 - Ages 35–60 years
 - BMI between 30-39 kg·m²
 - Sedentary (less than 30 min of physical activity/week during last 6 months)
 - Weight stable (no more than 5% change in body weight the previous 3 months)
 - >5% risk for a cardiovascular event in the next 10 years according to the 2013 American College of Cardiology/American Heart Association risk calculator and/or 2 out of 5 metabolic syndrome risk factors (Triglycerides \geq 150 mg/dL; HDL \leq 40 mg/dL; Glucose \geq 100 mg/dL; Waist Circumference \geq 102 cm for males, 88 cm for females; Blood pressure: \geq 130 mmHg systolic and/or 85 mmHg diastolic or being treated for hypertension).
 - Stable doses of medications for 90 days
 - Willing to stop all NSAIDs and aspirin for 7 days prior to muscle biopsy
 -
- ii. Exclusion Criteria
 - Smoking
 - Previous use of statins
 - Use of other medications or supplements that affect lipid profiles or body weight in the last 6 months
 - e.g., fibric acids, bile acid sequestrants, nicotinic acids, fish oil
 - Diagnosis of chronic diseases including CVD, diabetes, other metabolic diseases (e.g., thyroid), cancer, HIV, or acquired immunodeficiency syndrome
 - History of abnormal bleeding problems
 - Currently taking (within the last 10 days) anti-platelet medication (Plavix), Warfarin, and other anti-coagulants (eliquis, pradaxa, and xarelto) medications.
 - >2 fold upper normal limit (UNL) for ALT or creatinine
 - Women who are pregnant or breastfeeding
 - Individuals with polymorphisms (SLCO1B1) known to be associated with susceptibility for statin induced myopathies (tested at screening)
 - Currently enrolled in another research study

b. Withdrawal/Termination criteria: Subjects are free to abstain from taking their statins and leave the study at any time. We will test both muscle enzymes (creatinine kinase) and liver enzymes (ALT) to determine if statins are causing either muscle myopathies or liver injury. This testing will occur at baseline and at 1 month into taking statins. If enzymes are elevated, the subject will be taken out of the study for their own health.

E. Specific methods and techniques

This study will require approximately 13 total study visits plus exercising 5 times per week. The total time commitment of study visits is approximately 30 hours over the 12 weeks of study participation.

a. Testing Procedure

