- v. **Near InfraRed Spectroscopy (NIRS):** Muscle mitochondrial functional capacity will be measured non-invasively using a NIRS technique developed by [name], a member of the research team at ECU (46). Participants will perform submaximal knee extension exercise to increase muscle oxygen consumption (mVO_2) and the recovery kinetics is determined during a series of repeated arterial occlusions. The mVO_2 data are fit to a mono-exponential function to calculate the rate constant, which is directly related to the mitochondrial respiratory capacity. NIRS will be repeated at week 12.
- vi. **Pain Assessment:** Pressure pain threshold will be objectively assessed by a computerized algometer at rest and after exercise (73). In addition, we will ask participants to rate their current and usual whole body muscle pain while resting and moving using 0-10 numeric scales (0 = no pain, 10 = most intense pain imaginable) at different time points. We will ask the participants to rate the highest pain felt immediately and for up to 30 minutes after each maximal exercise test, as well as 24 hours later. Pain assessments will be repeated at week 12.
- vii. **Muscular Strength Assessment:** Knee isometric strength will be assessed using a Biodex dynamometer. Participants will be seated in a specialized chair and leg will be strapped to the dynamometer arm. Participants will also be secured to the chair to ensure isolation of the knee joint. Trained staff will instruct participants on how to gradually develop force in one second. Following 3 practice trials of submaximal contraction of both flexion and extension, participants will be asked to alternate between maximal flexion and extension with 60 seconds rest between contractions. There will be 3 trials of flexions and extension on both legs. Muscular strength assessments will be repeated at 1, 6, and 12 months
- viii. **Physical Performance Assessment:** A series of physical performance measurements will be performed to access balance, gait speed, and strength (74). The physical performance will be repeated at week 12.
- ix. **Body Composition:** Participants will be evaluated with dual energy x-ray absorptiometry (DEXA, Lunar Prodigy, version 11.2068, Madison, WI) to determine fat-free mass, fat mass and percent body fat at. DEXA uses very low X-ray doses (0.02mREM) to detect changes in body composition. DEXA body composition will be repeated at week 12.

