- x. **Exercise Testing:** Whole body steady state submaximal O_2 consumption will be determined during a standard 6 min treadmill test (2.5 mph) to determine VO_2 cost. Subjects will then complete a ramped treadmill test (Bruce protocol) to determine cardiorespiratory fitness (VO_2 peak) and peak heart rate as previously

described (13). We will also investigate post exercise oxygen consumption and heart rate at 60, 90, 120, and 300 seconds after cessation of the max test to determine if exercise recovery is impacted by statins. Blood will be sampled for measurement of CK 20-30 minutes following the maximal exercise to assess potential muscle damage. Exercise testing will be repeated at week 12.

- xi. Cardiovascular Function: These measures include both heart rate and stroke volume performed under both resting and sub-maximal exercise conditions (performed on separate days). Stroke volume will be estimated by finometer placed on finger (80). Cardiovascular function will be repeated at week 12.
- xii. Physical Activity Monitoring: Physical activity levels and sedentary time will be assessed by pedometers and accelerometers (BodyMedia Sensewear) (75, 76) for 5 day periods. Physical activity monitoring will be repeated at week 12.
- xiii. Statin Therapy Intervention: Once participants have successfully completed baseline testing, the participant will be randomly assigned to 1 of 3 groups (1:1:1 ratio). Statins will be prescribed as a placebo or at a dosage of 20 or 80 mg/day (atorvastatin; Lipitor) by the study physician at KUMC, [name], MD. Subjects and research team will be blinded to the type and dose of statin. Statins will be dispensed by the KUMC Investigational Pharmacy at regular intervals during the participant's enrollment in the study. The study physician will provide care for any problems associated with the statin treatment after un-blinding by the chair of the Data Safety Monitoring Board, [name]. All doses fall within the norms of recent recommendations and are given chronically (2)

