- xiv. Aerobic Exercise Intervention: Exercise training will be performed as done previously (13) and will consist of brisk walking and/or slow jogging on a treadmill 5 d each week at approximately 65-75% of each subject's VO₂peak, 45 min/session, at an energy expenditure of 1800-2000 kcal/wk, for 12 weeks. The exercise training will follow a three-stage progression: 1. wk 1=30 min, 3 d/wk, 60% VO₂max; 2. wk 2=30 min, 5 d/wk, 60% VO₂max; and 3. wk 3-12=45 min, 5 d/wk, 60-75% VO₂peak. Exercise intensity for each session will be monitored using heart rate monitors every 5 minutes and at least four exercise sessions per week will be supervised within KUMC exercise facilities.

F. Risk/benefit assessment:

a. Potential risks:

- i. Exercise: Some risks are associated with the exercise testing used to assess maximal aerobic capacity. Cardiovascular events during maximal exercise and in recovery are possible but rare in this population (1). However, these risks could be serious. Therefore, initial screening by maximal stress test will be performed in a clinical setting under the direction of a medical monitor (medical monitor only supervises the graded exercise test). Muscle soreness and strain are possible with exercise testing and training, but these are not a serious risk. The maximal aerobic capacity test represents greater risk of cardiovascular events than the training exercise because of the increased intensity of the exercise. However, events are extremely rare, and subjects will be screened for risk of cardiovascular disease and symptoms. Emergency equipment, including defibrillator, and ambulance plan are available for all subjects. Exercise training will be monitored by trained study staff to reduce risk.

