B. Expected Outcomes: The EX+Plac group and EX+Atorva20 groups will have a significant increase in VO₂peak, stroke volume, and a lowering of resting heart rate, common responses to exercise training. Measures of mitochondrial content (citrate synthase) and function (in-vivo NIRS, and ex-vivo respiration) will improve following the intervention, and will be preceded by increases in transcription factors (PGC-1 α , NRF-1, NRF-2, mTFA) known to control mitochondrial biogenesis measured at 1 month. Insulin sensitivity will also improve in the EX+Plac and Ex+Atorva20 groups. In contrast, the EX+Atorva80 group will display diminished mitochondrial and cardiorespiratory adaptations because of compromised respiratory capacity and disturbances in redox balance in skeletal muscle. This may occur due to a blunted exercise induced increase in PGC-1 α which is known to up regulate anti-ROS defense enzymes (101). Other cardiovascular adaptations may not improve in the EX+Atorva80 group, which could be due to impaired mitochondria oxygen consumption. We expect measures of pain and function to be triggered by the combination of exercise and Atorva80 treatment. These findings would indicate that higher dose atorvastatin impair exercise adaptations and that physicians should consider prescribing lower dose atorvastatin to patients who plan to utilize exercise training to lower cardiovascular risk. If these findings occur we will have remaining tissues to examine further mechanisms including if these findings are associated with reduced cellular ubiquinone levels, and altered balance between pathways controlling autophagy and apoptosis (Bcl-2 and Bax). These can be further supported by immunofluorescent examination of muscle fiber type changes and quantification of apoptosis by TUNEL staining. Given that a rodent study showed atorvastatin therapy blocked exercise induced increases in Glut4 mRNA and glycogen content (102), and that mitochondrial adaptations are critical for improved insulin sensitivity, we expect the EX+Atorva group will also display impaired improvements in insulin sensitivity.

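### The knee dynamometer test is repeated at 1, 6 and 12 months in a 12-week trial, so as written this measure has no end-of-training value

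*Combined protocol and SAP*

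**What the plan says.** Section II.E.a.vii defines the measure: "Knee isometric strength will be assessed using a Biodex dynamometer". It covers maximal flexion and extension, three trials each, on both legs. Its timing sentence is "Muscular strength assessments will be repeated at 1, 6, and 12 months".

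The rest of the plan describes a shorter study. Section II.B randomises participants to placebo or one of two atorvastatin doses "during a 12-week aerobic exercise training protocol". Section II.E states: "The total time commitment of study visits is approximately 30 hours over the 12 weeks of study participation". The last training stage in section II.E.a.xiv is "wk 3-12=45 min, 5 d/wk, 60-75% VO₂peak".

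The assessments around item vii follow that 12-week frame. For physical performance (item viii): "The physical performance will be repeated at week 12". For VO2peak (item x): "Exercise testing will be repeated at week 12". NIRS, pain, DEXA, cardiovascular function, activity monitoring and the IVGTT are also repeated at week 12. Biopsies and fasting bloods are repeated at weeks 4 and 12.

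Month-based timing survives in three other places:
- Section II.B refers to a one-year dose-response.
- Section II.E.a.iii places CK and ALT at 6 and 12 months and gives a blood volume for a twelve-month intervention.
- Section V.A sets the within-subject time factor at months 0, 1, 6 and 12.

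**The concern.** A schedule in the methods section is an instruction to site staff. Read literally, item vii asks for one strength test early in training and two after participants have left the study, and for nothing at the visit where almost everything else is measured.

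The measure is relevant to the trial's question. The abstract lists muscle weakness among the most commonly reported statin side effects and says that incidence rises with dose and duration. The statin risk section (II.F.a.ii) cites a trial of atorvastatin 80 mg in which about 15% of participants had pain and weakness. A test at about week 4 gives only an early look at an effect that is said to grow with time, and it cannot be paired with the week-12 VO2peak or NIRS result. Tests at 6 or 12 months would come well after the drug and supervised training described here had ended. A week-12 test that is missed cannot be recovered once a participant has finished.

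**Working it through.** The plan gives no figure to reproduce. The check sets the listed visits against the study window.

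**Inputs**
- Strength repeats: months 1, 6 and 12 (II.E.a.vii).
- Treatment and training: 12 weeks (II.B; II.E.a.xiv, last stage ends at week 12).
- Participation: 12 weeks (II.E).

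**Conversion**

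Weeks per month = 365.25 / 12 / 7 = 4.35.

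| Listed visit | Week | Position relative to week 12 |
|---|---|---|
| 1 month | 1 × 4.35 = 4.3 | inside the window |
| 6 months | 6 × 4.35 = 26.1 | 26.1 − 12 = 14.1 weeks after the end |
| 12 months | 12 × 4.35 = 52.2 | 52.2 − 12 = 40.2 weeks after the end |

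In the other direction, week 12 is 12 / 4.35 = 2.76 months, which matches none of the listed visits. The number of end-of-training dynamometer tests scheduled within participation is therefore 0.

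**How early the one in-trial test is.** Weeks 1 and 2 use 30-minute sessions, and the 45-minute stage begins in week 3. At week 4.3 a participant has completed about 4.3 − 2 = 2.3 weeks of the 10-week main stage.

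**Could another passage supply the missing visit?**
- No other section gives a dynamometer schedule, and none describes a follow-up phase after week 12.
- Section V.A does not help. Its time factor lists the same months, so it has no level for a week-12 value. Correcting V.A alone would not create the test, and correcting item vii alone would leave the week-12 value without a matching time level in the model.
- Item viii does supply something. It describes a battery covering balance, gait speed and strength, repeated at week 12. The text does not say what the strength task is, so the battery cannot be assumed to yield knee flexion and extension force. It is still end-of-training information on strength.

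**Does it reach the objectives?** The primary objective (II.A.a) is VO2peak. Secondary objective ii (II.A.b) has physical function in its heading, but the measures under it are DEXA, pressure thresholds, pain ratings and activity. Knee strength is not named. The sample size in II.C rests on VO2peak alone.

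**The case against.** The strongest reply is that this is text left over from a longer design. Every neighbouring item uses week 12, the same months recur in II.B, II.E.a.iii and V.A, and no 6- or 12-month phase exists for participants to attend. On that view staff would simply test strength at the final visit. This explanation of the error is plausible. It does not correct the text: item vii is the only place that schedules the test, and a reader cannot tell from it that one is due at week 12.

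A second reply is that little depends on the measure, and most of this stands. A reader might infer that the trial will have no end-of-training strength data at all, or that it cannot test its own prediction: "We expect measures of pain and function to be triggered by the combination of exercise and Atorva80 treatment". The documents do not support either inference. The item viii battery includes strength and is repeated at week 12. Pain is also repeated at week 12, so the prediction on pain and function can be examined without the dynamometer. That prediction does not name knee strength.

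A third reply is that the month-based time factor in V.A matters more, because it governs the primary outcome and every other one. That is fair, and the two should be corrected together. It is not a reason to leave item vii as it is.

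**Conclusion.** The inconsistency is real and confined to one measure. Followed as written, the Biodex knee isometric test has a single repeat inside the trial, at about week 4, and no end-of-training value for any participant. Two of the three listed repeats fall outside the participation that the plan describes. They are not shown to be impossible, but nothing in the plan provides for them.

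The primary VO2peak outcome, the sample size and the named secondary objectives are unaffected. What is lost is a separately planned, force-based measure of knee strength at the time point where it could be compared between arms and set beside the week-12 VO2peak and NIRS results.

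This rests on three readings of the text: that item vii's wording implies a baseline test, that participation ends at week 12 as II.E states, and that no visit schedule outside these documents already places the test at week 12. If such a schedule exists, only the wording needs correcting. The point is worth fixing because the correction is simple and the missing data could not be recovered later. It is better treated as an inconsistency in the text than as a deliberate design decision.

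**What to change.** 1. In II.E.a.vii, replace the three month-based times with visits that exist in this study: week 12, plus week 4 if the 1-month test is to be kept.
2. In V.A, restate the time factor in the weeks at which each outcome is measured, so that the week-12 strength value enters the between-arm model. If only week 12 is kept, strength has one follow-up time and the comparison becomes the baseline-adjusted week-12 difference between arms.
3. In the same amendment, reconcile the other month-based timings with the 12-week schedule: the one-year dose-response in II.B, and the CK/ALT times and twelve-month intervention in II.E.a.iii. The CK/ALT times concern safety monitoring. The passages contradict each other, and the investigators must settle them.

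The cost is a short text amendment. Item vii ends with one or two repeat tests instead of three, at time points when participants are already assessed, with no change to the sample size. It should be made before participants reach week 12.

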- a. Key personnel:** [name], [name], [name], [name], study physician at KUMC and [name], study physician at ECU.
- b. Plan for safety monitoring and review:** [name] will serve as the Chair of the Data Safety Monitoring Board and will convene every 6 months with the other members, Drs. [name] and [name] to make decisions on safety of the participants. Enrollment data will also be reviewed twice a year by the DSMB. In addition, data will be reviewed on a yearly basis with the biostatistician, [name] to determine if the studies should be shortened due to either no measured effect or due to effects that are greater than what power calculations indicated. If problems occur with participants, blinded study staff will alert [name]. [name] will have access to dose and type of statin and will consult the study physicians cardiologist to make a decision on whether the subject should be removed from the study for safety concerns. The PI and other key personnel will be examining research data on a subject to subject basis to ensure it is accurate and to address any potential problems that may arise with the protocols. In addition, Drs. [name] and [name] will discuss data at least once per month through in person meetings or by phone to ensure that data collection is occurring in a consistent manner at both locations.**Plan for adverse event reporting:** Adverse events will be defined as any untoward medical occurrence in study participants or others immediately involved in the performance of the protocol, which does not necessarily have a causal relationship with the study treatment, but results in a change in intervention, daily function, hospitalization or rated category 3 or above using the National Cancer Institute Common Terminology Criteria for Adverse Events (CTCAE) v3.0. Expected events such as slight muscle soreness consistent with statin therapy, or those consistent with a participant's prior medical history not sufficient to alter the intervention will not be considered an AE. Staff involved in performance of the protocol (e.g. coordinators) will continually monitor participants for adverse events throughout the intervention, and study staff will assess adverse events at every testing visit as well as during regularly scheduled telephone assessments with all randomized participants.

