If study staff, tester, or participant reports adverse events or complaints, relevant information will be collected and documented. The participant will be evaluated by the unblinded investigator identified in the protocol. The investigator will determine the severity (according to the CTCAE) and relatedness of the AE to the intervention. The investigator will identify adverse events of clinical concern, those that may require further workup, or suggest that additional participation in the intervention might be a safety risk. These AEs will first be discussed with the participant and then communicated to the study staff or providers with participant's consent and as appropriate. Serious adverse events directly related to study intervention will be reported immediately to the IRB. Any adverse event rate over 30% in 12 mo will be reported to the NIH.

III. Subject Participation

A. Recruitment:

- a.** Subjects will be recruited from the KUMC campus, from hospitals and clinics associated with KUMC and metro-Kansas City, Kansas and Missouri areas. Recruiting will occur through physicians and clinics and through advertisements in emails, flyers, newspaper

ads, radio spots, etc. Interested subjects will call or email and undergo initial phone screening, conducted by trained study staff, to see if they qualify. Should they meet the initial qualifications, they will come to the lab for an informed consent meeting with the PI, research coordinator, or other study staff. They will then be provided with an informed consent that is fully approved by the IRB at KUMC to review prior to the in-person meeting. Subjects who are interested in taking part in the study will be asked to sign the informed consent in the presence of a witness. Participants will have adequate opportunity to review the informed consent and to ask any questions they may have about the research protocol, compensation, risks, and benefits of taking part in the study.

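### Adverse events are graded and attributed, and discretionary removals decided, by people with access to the dose; the plan provides for no blinded judgement first

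*Combined protocol and SAP*

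**What the plan says.** Section II.B calls the design double-blinded, with arms of placebo, 20 mg and 80 mg atorvastatin. Section II.E.a.xiii adds: "Subjects and research team will be blinded to the type and dose of statin". On treatment of drug problems, the same item says: "The study physician will provide care for any problems associated with the statin treatment after un-blinding by the chair" (of the Data Safety Monitoring Board).

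Section II.K sets out two routes once something goes wrong.

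- **Adverse event reporting.** A report from staff, a tester or the participant starts the process. Complaints are included and no severity threshold is set. Information is gathered and written down, and then: "The participant will be evaluated by the unblinded investigator identified in the protocol. The investigator will determine the severity (according to the CTCAE) and relatedness" to the intervention.
- **Safety monitoring.** "If problems occur with participants, blinded study staff will alert" a named person (the name is removed), who "will have access to dose and type of statin and will consult the study physicians cardiologist to make a decision on whether the subject" should leave the study.

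The section counts an untoward occurrence as an adverse event if it "results in a change in intervention, daily function, hospitalization or rated category 3 or above" on the CTCAE scale. It exempts "Expected events such as slight muscle soreness consistent with statin therapy". On reporting it says: "Serious adverse events directly related to study intervention will be reported immediately to the IRB". A rate above 30% in 12 months goes to the NIH.

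Two other ways out of the study do not rest on this judgement. Removal for elevated muscle or liver enzymes is stated as a rule (II.D.b, repeated in II.F.a.ii), and participants may leave when they wish.

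**The concern.** Grade, relatedness and the decision to stop a participant are matters of judgement, and relatedness is the most exposed of the three. Section II.F.a lists muscle soreness and strain as a risk of exercise testing and training, and muscle pain, cramping and fatigue as a risk of statins. Every arm exercises. The same sore legs can therefore be put down to training or to drug, and an assessor who knows whether the participant takes placebo or 80 mg has a ready reason to choose.

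At stake is the credibility of the safety record by arm. Section V.B expects pain and function to be affected by exercise combined with 80 mg, and says the expected findings would lead physicians to consider lower doses. A dose pattern in adverse events would be read in that light. If the labels were assigned with the dose known, nobody could later tell how much of the pattern came from the labelling, and the missing blinded judgement could not be recovered.

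**Working it through.** The plan gives no figure on this point, so the check is mainly of the text.

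**1. Who is blinded.** Sections II.B and II.E.a.xiii: participants and research team.

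**2. Who grades and attributes.** In II.K, the sentence naming the unblinded investigator is followed directly by one in which the investigator sets severity and relatedness. The natural antecedent is the unblinded investigator. A second, blinded investigator is grammatically possible, but no section names one.

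**3. Who decides discretionary removal.** In II.K, a person with dose access, in consultation with the study physicians. The role given to blinded staff here is to raise the alert.

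**4. Whether a blinded judgement comes first.** Two provisions come closest. Information is documented before the unblinded evaluation, and study staff assess events at each testing visit and by telephone. Neither assigns staff a CTCAE grade, a relatedness call or a recommendation on removal. So a contemporaneous record exists, but the plan does not provide for a blinded judgement.

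**5. Where each judgement is used.**

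| Judgement | Use in the plan | Can it change what is counted or reported? |
|---|---|---|
| CTCAE grade | Category 3 or above is one entry criterion for an adverse event | Yes, the count |
| Removal | A change in intervention is another entry criterion | Yes, the count |
| Relatedness | Selects the serious events sent immediately to the IRB | Yes, expedited reporting; not the count, because the definition does not require a causal link |

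Thus two of the four entry criteria can turn on a judgement made with the dose known. The definition does not itself name who rates the category, so this rests on step 2.

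**6. Scale of one event.** Section II.C plans 120 enrolled, or 120/3 = 40 per arm. Section II.B caps randomisation at 80, or 80/3 ≈ 27 per arm. One event counted or not counted moves an arm's proportion by

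- 1/40 = 2.5 percentage points, or
- 1/27 = 3.7 percentage points.

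This shows how coarse the arm-level proportions are. It does not estimate bias: the documents do not say how often knowing the dose would change a call.

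**The case against.** The strongest defence is that the arrangement serves safety and limits the spread of dose knowledge. The protocol treats muscle side effects as dose-dependent, so the dose is relevant to whether someone should stop. Blinded staff pass problems to one person, which keeps the allocation from the rest of the team, and the study physicians are consulted. All of this stands, and it justifies dose access for the final removal decision. It does not require the grade and attribution to be made with the dose known.

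A second defence is that little depends on these labels. Section V.A plans no adverse event comparison by arm, and muscle harm is also captured by pain scales, algometry and CK outside this route. That limits the consequence. It does not replace grade, relatedness or removal, which section II.K still uses for counting and reporting.

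Third, blinded staff do document reports before the unblinded evaluation. That also stands: a reader should not infer that nothing is on file beforehand, only that no blinded grade, attribution or recommendation is asked for.

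A reader might also be tempted to take the rate of about 15% with pain and weakness on 80 mg in II.F.a.ii and work out how far a few changed calls would shift the arms. The documents do not support this. That figure is a symptom rate from another trial, not a rate of adverse events as defined here, and a change in relatedness alone would alter neither the count nor the 30% trigger.

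**Conclusion.** The point holds as a weakness in a stated procedure. In a trial described as double-blinded, grade and relatedness (on the natural reading) and discretionary removal are judged with the dose known or available, and the plan provides for no blinded judgement beforehand. Assessor bias could enter the count of adverse events through grade and removal, and expedited IRB reporting through relatedness. Any later summary by arm would carry the same doubt. Size and direction are unknown; step 6 of the working gives only the weight of a single event.

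Three stronger readings go beyond the documents.

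- **That the VO2peak comparison is biased.** This would need removals beyond those a blinded clinician would make, and nothing shows that such removals would occur or in which arm.
- **That the 30% NIH trigger would be missed or wrongly reached.** No figure in the documents supports this.
- **That the unblinded investigator has a particular identity or expectation, or applies the slight-soreness exemption knowing the dose.** Names are removed, and the text does not say who applies the exemption.

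The conclusion assumes that the investigator who grades is the unblinded one named in the sentence before. Label: cheap improvement.

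**What to change.** Amend the adverse event text in II.K and the case form as follows.

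- Before the code is opened, a clinician who is still blinded records CTCAE grade, relatedness and a remove/continue recommendation.
- The study physician can do this if II.E.a.xiii means that this person stays blinded until the DSMB chair breaks the code. Because names are removed, the sponsor should confirm this or name another blinded clinician.
- Unblinding is allowed immediately whenever care requires it, with the date and reason logged.
- The final removal decision stays with the person who has dose access, in consultation with the study physicians, as now.

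The cost is a change of protocol wording, one form change and one short extra recorded step per event, waived in an emergency. If no study physician is in fact still blinded, a blinded clinician must also be assigned.
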